7.8 CA-125

The CA-125 at baseline and post-baseline assessments, and maximum changes in CA-125 from baseline among all post baseline assessments will be summarized. Number of subjects with >=50%, >=75% and 100% decreases or increase from baseline will be summarized. The percent change from baseline in CA-125 for all post-baseline assessments will be plotted by subject. The CA-125 test results along with change from baseline will be presented in a data listing.

8. SAFETY ANALYSES

Unless specified otherwise, all safety data summaries will be presented by dose schedule/level, and all subjects based on the All Treated population. Summaries will also be provided for pooled subjects at the same dose level. safety summary will be provided for DLT evaluable populations.

8.1 Maximum Tolerated Dose Evaluation

The MTD evaluation will be based on the DLT Evaluable Population. The number and percentage of subjects with DLT will be presented by dose schedule and level for dose escalation cohorts. The MTD level will be indicated in the summary.

The MTD will be estimated using isotonic regression (based on the DLTs observed in the DLT evaluable subjects). A MAD will be reported if the DLT rate never reaches $\geq 25\%$. Otherwise, an MTD will be reported. Isotonic regression is a way to estimate the MTD under the assumption that toxicity increases with dose. When using isotonic regression, the first step is to identify the doses where the dose-toxicity monotonicity assumption is violated. The DLT estimate is then adjusted for the violators such that the final estimate of the DLT rate increases with the dose. The target DLT rate is then used to select the MTD. For example, suppose that when the trial is completed, the observed DLT rates [# subjects who experienced DLT]/[# evaluable subjects] at five dose levels are (0/3, 1/3, 0/3, 4/15, 2/4). In this example the observed DLT rate at Dose Level 2 (i.e., 1/3=33%) is higher than the observed DLT rate at Dose Level 3 (i.e., 0/3=0%). To adjust for this violation, the DLT estimates are replaced with their average, i.e., (1/3+0/3)/2=1/6, resulting in the isotonic regression DLT estimates (0/3, 1/6, 1/6, 4/15, 2/4) = (0%, 16.7%, 16.7%, 26.7%, 50%), which monotonically increases with the dose level. Based on this isotonic estimate, assuming that the trial goal is to find the dose with the DLT rate of 30%, Dose Level 4 will be selected as the MTD. If there are no violators of the dose-toxicity monotonicity assumption, isotonic regression directly uses the observed DLT rates as the final estimates for MTD selection. For subjects who undergo intra-subject dose escalation, only DLTs that occur during the DLT period on the subject's initial dose level the assignment will be used for MTD determination.

In the case of dose levels with estimated toxicity of equal distance (tied dose levels) from the target toxicity of 30%, the following approach will be used: among all tied dose levels the highest dose level with target toxicity \leq 30% will be selected, unless all tied dose levels have estimated toxicity \geq 30%, in which case the lowest dose level will be selected.

8.2 Adverse Events

The AE terms on the eCRFs will be mapped to the preferred terms (PT) and system organ classes (SOC) using the Medical Dictionary for Regulatory Activities (MedDRA). Drug-related AEs are defined as AEs with relationship to study treatment being related or possible related. A worst-case scenario approach will be taken to handle missing data, i.e. AEs with the relationship to study treatment as missing will be treated as drug-related AEs.

All AEs with onset dates on or after the first dose of study treatment are defined as treatmentemergent adverse events (TEAEs). Only TEAEs will be included in AE tables.

An overview summary of TEAEs will be produced to include counts and percentages of subjects with any TEAE, drug-related TEAEs, DLT, serious TEAEs, drug-related serious TEAEs, fatal TEAEs, immune related TEAEs, infusion related reaction AEs, Grade 3 or 4 TEAEs, and TEAEs leading to drug withdrawn, drug interrupted, dose not given/held, and infusion interrupted.

The TEAE by maximum toxicity grade summary tables will use the following algorithms for counting subjects:

- **PT rows:** each subject is counted once within each unique PT at the maximum grade. For example, if a subject has two headaches, the subject is counted only once under the PT "Headache". Subjects experiencing the same TEAE PT several times with different grades will only be counted once with the maximum grade.
- **Any event row**: each subject with at least one TEAE will be counted only once at the maximum grade no matter how many events they have.

All TEAEs and drug-related TEAEs will be summarized by MedDRA PT and maximum toxicity grade. The PT will be ordered by descending order of the subject incidence based on all subjects in the analysis population. A table of all TEAEs by SOC and PT will also be provided.

The following summary tables will be presented by MedDRA PT, in which the PT will be sorted by descending order of subject incidence of PT based on all subjects in the analysis population:

- Summary of all TEAEs.
- Summary of drug-related TEAEs.
- Summary of Grade 3 or 4 TEAEs.
- Summary of DLT.
- Summary of TEAEs leading to drug interrupted, dose not given/held, infusion interrupted, and drug withdrawn.
- Summary of serious TEAEs.
- Summary of drug-related serious TEAEs.
- Summary of immune related TEAEs.

Additional summaries for drug-related IRR AE (toxicity grade, seriousness, number of events, action taken) at event-level, at subject-level, and number of subjects with IRR at each dosing visit among the first two cycles and during all subsequent cycles combined will be provided.

All AEs, immune related AEs, drug-related AEs, Grade 3 or 4 AEs, drug-related Grade 3 or 4 AEs, DLTs, SAEs, fatal AEs, AEs leading to dose not given/held, infusion interruption, dose increased or dose reduced, and drug withdrawal, and infusion related reaction signs and symptoms will be presented in data listings. Pretreatment AE, defined as AEs that start prior to the first dose of the study treatment, will be flagged in relevant listings. All AEs for the Screen Failures population will also be presented in a data listing.

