- Screening: Screening Period extends from Day -21 to Day -1. The following screening assessments must be performed within 72 hours of the first dose of SL-172154: hematology profile, chemistry profile, coagulation profile, ECOG score, physical exam, and pregnancy test. Baseline CT or positron emission tomography (PET)/CT or Magnetic resonance imaging (MRI) tumor assessments are required for all subjects within 28 days prior to the first dose of SL-172154. a.
- Assessment Window: With the exception of Screening assessments and unless otherwise specified, assessments performed at < 3-week intervals will have a +/- 3-day window and assessments performed at > 3-week intervals will have a +/- 1-week window. Assessments throughout the study are calendar based starting from the first day of dosing (day 1) in the first treatment period. Dose interruptions should not alter the assessment schedule for any subsequent treatment period. р.
- Inclusion/Exclusion criteria: Subjects must meet eligibility criteria prior to first dose of SL-172154 on C1D1. i
- Vital Signs: Blood pressure (BP), heart rate (HR), temperature (T) and respiratory rate (RR) must be measured after the subject has been sitting for at least five minutes (min). Pulse oximetry will be collected to coincide with vital sign time points noted below. d.
- and 15 min (\pm 5 min), 0.5 hour [hr] (\pm 5 min), 1 hr (\pm 10 min), 1.5 hr (\pm 10 min) 2 hr (\pm 10 min), 4 hr (\pm 10 min), and 6 hr (\pm 10 min) after start of Collect vital signs/pulse oximetry during Cycle 1 on D1, D8, D15 and Cycle 2 on D1 and D15: Predose (within 30 min of starting the infusion) infusion (SOI). 1
- Vital signs/pulse oximetry should be taken once prior to scheduled PK samples on C1D2, C1D3, C1D16 and C2D2 5
- Collect vital signs/pulse oximetry on dosing days \geq C3D1: Predose (within 30 min of starting the infusion) and at the end of infusion [EOI] (± 2 mm) 3)
- within 72 hrs of starting SL-172154. Repeat this test every 8 weeks during SL-172154 treatment (i.e., C3D1, C5D1, C7D1, etc.). Contraception should be Pregnancy Test: A serum pregnancy test (beta-human chorionic gonadotropin [β-hCG]) or urine pregnancy test must be performed at screening for all FCBP continued for at least 30 days after the last dose of SL-172154. e.

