7. SAFETY ASSESSMENTS

Subjects will be followed continuously for all AEs starting when a subject has signed the ICF, throughout the course of treatment and for 90 days after the last dose of IP. After a subject is discontinued from SL-172154 due to progressive disease or for other reasons, any ongoing AEs should be followed until resolution (or return to baseline) and documented in the eCRF. If another anti-cancer agent is started within 90 days after the last dose of SL-172154, only SAEs and AEs that occur prior to starting the new anticancer therapy should be recorded. All observed or volunteered AEs (serious or non-serious) and abnormal laboratory test findings, if applicable, whether suspected to have a causal relationship to SL-172154 or not will be recorded in the subject medical record and in the eCRF. AEs will be graded according to NCI-CTCAE v5.0. For all AEs, sufficient information will be pursued and/or obtained to permit an adequate determination of seriousness and outcome of the event (i.e., whether it should be classified as a SAE or not) and an assessment of the causal relationship between the AE and SL-172154. AEs will be followed until resolution (or return to baseline) or stabilization. Refer to Section 7.4 for documentation and reporting of AEs.

Event	Definition
Adverse Event (AE)	The AE observation period starts at the time of signing informed consent and includes
	baseline or washout periods, even if no study treatment has been administered.
	An AE is defined as any untoward medical occurrence in a subject to whom the IP has
	been administered, regardless of whether the event is considered related to that product.

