7.3 Timing for Event Assessment and Follow-up

All AEs occurring while on study must be documented appropriately regardless of relationship. All AEs will be followed to adequate resolution. The occurrence of an AE or SAE may come to the attention of study personnel during study visits and interviews of a study subject presenting for medical care, or upon review by a study monitor.

Any medical condition that is present at the time that the subject is screened will be considered as baseline and not reported as an AE. However, if the pre-existing condition deteriorates at any time after the subject signs the main study ICF, it will be recorded as an AE. Unanticipated problems will be recorded in the data collection system throughout the study.

AEs characterized as intermittent require documentation of onset and duration of each episode.

Event	Reporting Procedures
Adverse Event	Subjects will be followed continuously for AEs during the study and for 90 days after the last dose of IP. After a subject is discontinued from IP due to progressive disease or for other reasons, any ongoing AE should be followed until resolution (or return to baseline) and documented in the eCRF, regardless of whether the event(s) is attributed to trial medication. If another anticancer agent is started within 90 days of the last dose of SL-172154, only SAEs and irAEs that occur before the new anticancer therapy should be recorded. The following information will be recorded: description, date of onset and end date, severity, assessment of relatedness to trial medication, and action taken. Follow-up information should be provided as necessary. AEs will be followed either until resolution, or the event is considered stable.
	It will be left to the Investigator's clinical judgment to decide whether an AE is of sufficient severity to require the subject's removal from treatment. A subject may also voluntarily withdraw from treatment due to what he or she perceives as an intolerable AE. If either of these occurs, the subject must undergo an end of trial assessment and be given appropriate care under medical supervision until symptoms cease, or the condition becomes stable.

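### The SAP's treatment-emergent definition has no worsening limb, so an AE that starts between consent and first dose and worsens on drug may be left out of the TEAE tables

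*SAP*

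**What the plan says.** SAP 8.2 classifies events by onset date alone: "All AEs with onset dates on or after the first dose of study treatment are defined as treatmentemergent adverse events". It then limits the tables: "Only TEAEs will be included in AE tables". Events with earlier onset go elsewhere: "Pretreatment AE, defined as AEs that start prior to the first dose of the study treatment, will be flagged in relevant listings".

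Protocol Section 7 starts collection before dosing: "Subjects will be followed continuously for all AEs starting when a subject has signed the ICF". Its definitions table agrees: "The AE observation period starts at the time of signing informed consent". The schedule of assessments gives the length of that window: "Screening Period extends from Day -21 to Day -1".

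On how events are recorded, Protocol 7.3 says: "AEs characterized as intermittent require documentation of onset and duration of each episode". Protocol 7.1.1 and 7.3 also say that a condition already present at entry or screening is not itself an AE, but that its later deterioration is recorded as one. Neither document has a rule for an AE that begins after consent but before first dose and then changes grade on treatment.

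The safety analysis in Protocol 9.2.4 plans frequency tables of AEs without a treatment-emergent restriction. That restriction is not among the four changes listed in SAP Section 11.

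**The concern.** Incidence of AEs, immune-related AEs and SAEs is part of the primary outcome in both documents. A treatment-emergent definition is meant to separate what happened before the drug from what happened on it. Without a worsening limb, it puts some on-drug deterioration on the wrong side of that line.

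The events at risk are those that arise in the screening window and are still present at dosing. Examples are a complication of the baseline biopsy, or pain or fatigue that begins or worsens between consent and Day 1. If such an event becomes Grade 3 or 4, serious or a cause of withdrawal on drug, the tables may not count it. The error runs in one direction, because the rule can remove such events but cannot add any. The result may also depend on how a site enters the event rather than on what happened to the subject.

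**Working it through.** The plan gives no figure to reproduce. The check sets the recording rules beside the tabulation rules.

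**Inputs**
- Recording starts at consent (Protocol 7); screening runs from Day -21 to Day -1, so up to 21 days (Protocol 6.1, footnote a).
- A TEAE needs onset on or after first dose, and only TEAEs are tabulated (SAP 8.2).
- The maximum-grade counting rule works within TEAEs (SAP 8.2), so it cannot bring back a record with pre-dose onset.
- Each AE record carries onset and end dates, severity, relatedness and action taken (AE reporting table in Protocol 7). A separate onset is required explicitly only for intermittent episodes (Protocol 7.3).

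**Cases**
1. *Condition present at screening and stable until dosing, then worse on drug.* Protocol 7.1.1 and 7.3 make the deterioration a new AE. Its natural onset is the date of deterioration, so it is a TEAE and is tabulated.
2. *AE new between consent and first dose, resolved before dosing.* It is a pretreatment AE and is properly left out of the tables.
3. *AE new in that window, or a baseline condition that deteriorates in it, ongoing at dosing and worse on drug, entered as a new record dated at the worsening.* It is a TEAE and is tabulated.
4. *The same event kept on its original record.* The onset is pre-dose, so it is not a TEAE. It is missing from the overview, preferred-term, maximum-grade, Grade 3 or 4, serious, drug-related and drug-withdrawn tables. It remains in the listings.
5. *Case 4, judged a DLT.* SAP 8.1 counts it with no onset condition. The DLT Evaluable definition in SAP Section 4 admits any subject with a DLT in the period. SAP 8.2 lists a DLT summary among its AE tables; whether the TEAE-only sentence governs that summary is not stated.
6. *Case 4, a laboratory abnormality or a death.* Laboratory worsening appears in the worst-case grade shift tables, which include unscheduled values (SAP 8.3). Deaths are summarized separately (SAP 8.4). Pain, fatigue or neuropathy has no equivalent table.

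Cases 3 and 4 describe the same clinical event and differ only in data entry. The documents do not say which applies.

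**Size per subject.** One subject missing from a row with n treated subjects lowers that row by 1/n. With 3 subjects this is 1/3 = 33 percentage points; with 12 it is 1/12 = 8 points. SAP 5.2 pools the escalation, pharmacodynamic and expansion cohorts and also pools schedules at the same dose, so n can exceed 12 and the 8 points is not a minimum. A subject is lost from a row only if no other TEAE of theirs qualifies for it.

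**The case against.** The strongest reply is that the gap is narrow and mostly covered elsewhere. Much of this reply stands. Conditions that patients bring into screening are baseline under Protocol 7.3, and their deterioration is a recordable AE. A reader might infer that the SAP removes on-drug worsening of the disease- and treatment-related conditions typical of this population. The documents do not support that, because those conditions fall under case 1. Signs clearly due to expected cancer progression are not AEs at all (Protocol 7.1.1). Laboratory worsening and deaths have their own tables, and in a trial of 33 to 54 subjects the listings can be read in full.

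A reader might also infer that DLTs are lost, or that the MTD is biased. This is not supported either. SAP 8.1 and the DLT Evaluable definition apply no onset filter, and SAP Table 14.3.1.12 is titled and populated as a DLT table, without the treatment-emergent label. At most, one general sentence in 8.2 is in tension with 8.1.

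Finally, Protocol 7.3 does not say that a continuous AE must stay on one record. The eCRF completion rules could already require a new record. The loss is therefore possible, not certain. The reply does not remove the gap in the text: the SAP has no worsening limb, and nothing in either document guarantees that the worsening will be re-dated.

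**Conclusion.** The point holds in a limited form. An AE that begins or deteriorates between consent and first dose, continues to dosing, and then increases in grade or becomes serious on drug may be absent from the TEAE tables. This rests on one assumption that the documents leave open: that the worsening stays on the original record. The effect can only understate a primary safety outcome. The documents give no basis for the number of subjects affected, so no study-level estimate is offered; the per-subject effect depends on the dose-level denominator, as shown above. No dose decision, DLT count or MTD estimate under SAP 8.1 changes. The definition is still worth correcting, because the remedy is small and makes the tables independent of site entry habits.

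**What to change.** 1. In SAP 8.2, define a TEAE as an AE with onset on or after first dose, or with earlier onset that increases in CTCAE grade or becomes serious on or after first dose. Tabulate it at its post-dose grade.
2. In Protocol 7.3 and the eCRF completion guide, require post-dose worsening of a pre-dose AE to be recorded with the date of worsening.
3. In SAP 8.2, state that the DLT summaries include all DLTs regardless of AE onset date, consistent with 8.1.
4. Add the restriction of AE tables to TEAEs to the list of changes in SAP Section 11.

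The cost is some wording, queries on the few AEs that span first dose, and slightly higher reported rates.

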During the study while subjects are receiving treatment with SL-172154, SMC meetings will be held to review relevant data with the investigators or delegates. These meetings will be held once a month (or more frequently if required) during dose escalation to share safety data and communicate results of ongoing analyses. All available safety, PK, pharmacodynamic, and clinical outcome data for all subjects at the time of the scheduled SMC Meeting will be reviewed and summarized. Attendees of SMC meetings will include but not be limited to clinical investigators (or designees), the Sponsor Medical Monitor and Statistician. The SMC will operate in accordance with the SMC charter which will define roles and accountabilities and the process for safety review.

The Sponsor will remain in constant contact with the clinical sites during the enrollment period to ensure that cohort enrollment during the dose escalation of this study is completed as per protocol. All dose escalation or safety decisions made by the SMC will be documented in writing with copies maintained at each site and the Trial Master File at the Contract Research Organization.

Statistical Analyses

The safety evaluation will be based on the All Treated Population defined as all subjects who received at least one dose of study treatment. Frequency tables will be used to describe safety and tolerability parameters AEs, irAEs, SAEs, fatal SAEs and AEs leading to discontinuation of SL-172154. Changes in toxicity grade for clinical chemistry and hematology will also be summarized. AEs will be mapped to a Medical Dictionary for Regulatory Activities preferred term and system organ classification. Laboratory abnormalities will be graded according to the NCI CTCTAE v5., if applicable. The DLT evaluation will be based on the DLT evaluable population (defined as All Treated subjects enrolled in the dose escalation cohorts 1) who have received ≥ 2 of the 3 scheduled doses of IP during cycle 1 on Schedule 1 (or at least 2 of the 4 scheduled doses of SL-172154 on Schedule 2) and complete the safety follow-up through the 28-day DLT evaluation period; or 2) who experience any DLT during the DLT evaluation period). DLTs will be summarized by dose level. The MTD will be estimated using isotonic regression.

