9.2.4 Safety Analyses

The safety evaluation will be based on the All Treated Population and the DLT evaluation will be based on the DLT evaluable population.

DLTs will be summarized by dose level. Frequency tables will be used to describe safety and tolerability parameters AEs, irAEs, SAEs, fatal SAEs and AEs leading to discontinuation of SL-172154. Graphs may also be presented where appropriate. AEs will be mapped to a Medical Dictionary for Regulatory Activities (MedDRA) preferred term and system organ classification. Laboratory abnormalities will be graded according to the NCI CTCTAE v5., if applicable. Concomitant medications will be coded using the World Health Organization Drug Dictionary.

MTD: The MTD will be estimated using isotonic regression (based on the DLTs observed in DLT evaluable subjects). Specifically, the MTD is the dose for which the isotonic estimate of the DLT rate is closest to the target DLT rate of 30%. If two or more doses tie for the smallest difference, perform the following rules:

- If the estimated DLT rate < 30% for all doses, then select the higher dose among the tied doses;
- If the estimated DLT rate for the tied doses are a combination of < 30% for and > 30%, then select the higher dose among the tied doses;
- If the estimated DLT rate > 30% for all dose, then select the lower dose among the tied doses

NOTE: For subjects who undergo intra-subject dose escalation, DLTs will only be assessed during the DLT period applicable on the subject's initial dose level.

A MAD will be reported if the observed DLT rate is <25% among all dose levels. Otherwise, an MTD will be reported.

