5.2 Reporting Conventions

The statistical analyses will be reported using summary tables, figures, and data listings. The International Conference on Harmonisation (ICH) numbering convention will be used for tables, listings, and figures.

Data from all participating sites will be pooled prior to data summary or analysis. It is anticipated that subject accrual will be spread thinly across sites and summaries of data by site will not be informative and therefore, will not be provided.

Unless specified otherwise, all summary tables will be presented by dose schedule/level for all subjects in the analysis population, and subjects from dose escalation, pharmacodynamic and dose expansion cohorts will be pooled. Summaries will also be provided for subjects at the same dose level pooled across schedules. Select safety summary tables may be provided for the dose escalation cohorts.

All individual subject data listings will be presented by dose level, dose schedule and subject, unless specified otherwise. Data from all assessments, whether scheduled or unscheduled, will be included in the listings. Listings will present the data in their original format (without any imputation), unless specified otherwise.

Summaries by planned time point will include data from scheduled assessments and all data will be reported according to the nominal visit for which it will be recorded (i.e., no visit windows will be applied). Unscheduled data, when summarized, will be included only in calculation of the maximum or minimum value over time such as worst-case post-baseline. If multiple assessments are reported on the same date for the same scheduled planned time, the worst-case result will be analyzed.

Continuous variables will be summarized with means, standard deviations, medians, minimums, and maximums. The precision of the original measurements will be maintained in summaries and listings, when possible. Generally, means and medians will be presented to one more decimal place than the raw data, and the standard deviations will be presented to two more decimal places than the raw data.

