Categorical variables will be summarized by counts and by percentages of subjects in the corresponding categories. Percentages are routinely based on the total number of the specified population N if not otherwise specified. For frequency counts, categories whose counts are zero will be displayed for the sake of completeness. For example, if none of the subjects discontinue due to "lost to follow-up," this reason will be included in the table with a count of 0. Categories with zero counts will not have zero percentages displayed.

All confidence intervals (CIs) will be constructed at the 95% confidence level, unless specified otherwise.

All analyses and tabulations will be performed using SAS® v9.4 or above.

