13. APPENDIX: LIST OF TABLES, FIGURES AND LISTINGS

13.1 List of Tables

ICH Heading	Table Number	Table Description	Analysis Population
14.1		Demographics	
	14.1.1	Study Populations and Subject Disposition	All Screened
	14.1.2	Study Treatment Status	All Treated
	14.1.3	Protocol Deviations	All Treated
	14.1.4	Demographic and Baseline Characteristics	All Treated
	14.1.5	Study Cancer History	All Treated
	14.1.6	Prior Anti-Cancer Treatment	All Treated
14.2		Efficacy	
	14.2.1	Objective Response with Confirmation Based on RECIST 1.1	All Treated
	14.2.2	Objective Response with Confirmation Based on RECIST1.1	Response Evaluable
	14.2.3	Objective Response with Confirmation Based on iRECIST	All Treated
	14.2.4	Time to Response and Duration of Response Based on RECIST 1.1	Response Evaluable
	14.2.5	Time to Response and Duration of Response Based on iRECIST	Response Evaluable
	14.2.6	Progression-Free Survival Based on RECIST 1.1	All Treated
	14.2.7	Progression-Free Survival Based on iRECIST	All Treated
	14.2.8	Overall Survival	All Treated
	14.2.9	Tumor Assessment at Baseline	All Treated
	14.2.10	CA-125	All Treated
14.3		Safety	
14.3.1		Study drug exposure/adverse event	
	14.3.1.1	Study Drug Exposure	All Treated
	14.3.1.2	Overall Summary of Treatment-Emergent Adverse Events	All Treated
	14.3.1.3	All Treatment-Emergent Adverse Events by System Organ Class and Preferred Term	All Treated
	14.3.1.4	All Treatment-Emergent Adverse Events by Preferred Term and Maximum Toxicity Grade	All Treated
	14.3.1.5	Drug-Related Treatment-Emergent Adverse Events by Preferred Term and Maximum Toxicity Grade	All Treated
	14.3.1.6	All Treatment-Emergent Adverse Events by Preferred Term	All Treated
	14.3.1.7	Serious Treatment-Emergent Adverse Events by Preferred Term	All Treated
	14.3.1.8	Immune Related Treatment-Emergent Adverse Events by Preferred Term	All Treated

ICH Heading	Table Number	Table Description	Analysis Population
	14.3.1.9	Drug-Related Treatment-Emergent Adverse Events by Preferred Term	All Treated
	14.3.1.10	Drug-Related Serious Treatment-Emergent Adverse Events by Preferred Term	All Treated
	14.3.1.11	Treatment-Emergent Adverse Events with Toxicity Grade 3 or 4 by Preferred Term	All Treated
	14.3.1.12	Dose Limiting Toxicities	DLT Evaluable
	14.3.1.13.1	Treatment-Emergent Adverse Events leading to Infusion Interrupted by Preferred Term	All Treated
	14.3.1.13.2	Treatment-Emergent Adverse Events Leading to Dose Not Given/Held by Preferred Term	All Treated

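### The adverse event overview gives the DLT percentage on all treated subjects pooled over cohorts, so it can disagree with the DLT table for the same schedule and dose

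*SAP*

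**What the plan says.** The overview row is built from these parts of the SAP:

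- Section 8.2 makes DLT one of the rows of the treatment-emergent adverse event overview: "An overview summary of TEAEs will be produced to include counts and percentages of subjects with any TEAE, drug-related TEAEs, DLT".
- Section 8 sets the default population: "Unless specified otherwise, all safety data summaries will be presented by dose schedule/level, and all subjects based on the All Treated population".
- Section 13.1 lists Table 14.3.1.2, "Overall Summary of Treatment-Emergent Adverse Events", with All Treated as its population.
- Section 5.2 sets the denominator: "Percentages are routinely based on the total number of the specified population N if not otherwise specified". On the columns it says that "subjects from dose escalation, pharmacodynamic and dose expansion cohorts will be pooled".

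The DLT analysis is defined on another base:

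- Protocol 9.2.4 puts the safety evaluation on All Treated and, in the same sentence, says that "the DLT evaluation will be based on the DLT evaluable population".
- The protocol synopsis (Statistical Analyses) describes that population as "defined as All Treated subjects enrolled in the dose escalation cohorts" who also meet a dosing and follow-up condition or have a DLT. SAP Section 4 carries the same restriction to escalation.
- SAP 8.1 gives the DLT count and percentage by schedule and level for the escalation cohorts. Section 13.1 lists Table 14.3.1.12, "Dose Limiting Toxicities", on DLT Evaluable.

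SAP Section 11 records both the pooling of cohorts and the limitation of DLT Evaluable to escalation. It does not say what the two together do to the DLT row of the overview.

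**The concern.** For most rows of an adverse event overview, All Treated is the right denominator. DLT is different because being counted as free of DLT has conditions. Under SAP Section 4 a subject without a DLT is evaluable only if enrolled in escalation, given at least two cycle 1 doses and followed through the 28-day period. Two groups fail this and still sit in the All Treated denominator: pharmacodynamic and expansion subjects, and escalation subjects who were not evaluable. Protocol 9.1 lets the latter be replaced.

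DLT incidence is among the outcome measures for the primary objective. Followed as written, the plan lets one report give two percentages for it at the same schedule and dose, with no planned explanation of the difference. The gap is widest at dose levels that receive pharmacodynamic or expansion subjects, and these can include the potential RP2D.

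**Working it through.** **Inputs**

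- Escalation: 21 subjects (Schedule 1 only) or 42 (both schedules). Pharmacodynamic cohort: about 6. Expansion: about 6. Stated totals: 33 or 54. All from SAP 3.3.
- Goal at the potential RP2D: about 6 to 12 subjects over the three cohorts (SAP 3.1 and 3.3).
- DLT counts are not in the documents. Those used below are assumptions for illustration.

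**Step 1. Planned totals.** 21 + 6 + 6 = 33 and 42 + 6 + 6 = 54, as stated. In either case 12 planned subjects count in the All Treated denominator and cannot be DLT Evaluable.

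**Step 2. Numerator.** By the second limb of the SAP Section 4 definition, an escalation subject with a DLT in the evaluation period is DLT Evaluable. If DLTs are counted in escalation subjects only, both tables have the same numerator x and only the denominators differ.

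**Step 3. All-dose column.** Let N_E be the evaluable and N_T the treated subjects. The ratio of the overview percentage to the evaluable-based one is (x/N_T) / (x/N_E) = N_E/N_T. Taking every planned escalation subject as evaluable:

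| Plan | Ratio | Example with same x |
|---|---|---|
| Schedule 1 only | 21/33 = 0.64 | 3/21 = 14.3% against 3/33 = 9.1% |
| Both schedules | 42/54 = 0.78 | 6/42 = 14.3% against 6/54 = 11.1% |

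**Step 4. One dose level.** One DLT in 6 evaluable subjects is an escalate decision in SAP Table 2, so the level is cleared. Table 14.3.1.12 would show 1/6 = 16.7%. Adding 6 pharmacodynamic or expansion subjects gives 12 at that dose, within the planned range, and the overview would show 1/12 = 8.3%.

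**Step 5. Non-evaluable subjects alone.** One replaced escalation subject at that level, with no added cohort, gives 1/7 = 14.3% in the overview against 1/6 = 16.7%.

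**Step 6. DLT-type events flagged in every cohort.** SAP 8.2 does not restrict the row to escalation. With 3 DLTs among 21 escalation subjects and 2 such events among the 12 others, Table 14.3.1.12 gives 3/21 = 14.3% and the overview gives 5/33 = 15.2%. The overview is now the higher of the two.

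**Where the tables agree.** They match at a level with no flagged events, or where every treated subject is an evaluable escalation subject.

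**The case against.** The strongest reply is that the DLT analysis the protocol asks for is already on the right population. The interim DLT summary (SAP 5.1), the MTD evaluation (SAP 8.1), Table 14.3.1.12 and Listing 16.2.7.2 all use DLT Evaluable. On this view the overview adds a second, labelled incidence on the population the protocol uses for safety, and two labelled denominators are not a contradiction. The first part stands: nothing that drives a decision uses the overview row. The second part stands only in part. Protocol 9.2.4 separates the DLT evaluation from the rest of safety, and a population label on the whole table does not tell the reader that this row's denominator includes subjects outside the DLT evaluation.

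It can also be said that the pooling, the All Treated default and the percentage base all yield where something else is specified, and that the table shells are not among the documents. The shells might indeed carry a row-specific N. But no passage in either document specifies one for this row, so the defaults apply as the SAP is written.

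A third objection stands. Protocol 3.4 defines DLTs by type of event and the first 28 days of dosing, and the population table in protocol 9.2.1 has no escalation restriction. If events in pharmacodynamic or expansion subjects are flagged as DLTs, the overview is the only listed summary that would show them under that name. Deleting the row, or limiting it to evaluable subjects, would lose them unless they are shown elsewhere.

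**Conclusion.** The inconsistency holds as a reporting defect in a named primary outcome. It is minor and easily repaired. Its size depends on DLT counts that the documents do not give. The ratios of 64% and 78%, and the change from 17% to 8% at one dose, assume that DLTs are counted in escalation subjects only; the two ratios also assume that all planned escalation subjects are evaluable.

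Three stronger readings are not supported:

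- A reader might infer that dose decisions or the MTD are distorted. They are not, because escalation, MTD and MAD all rest on DLT Evaluable.
- A reader might infer that the overview always understates the rate and makes the selected dose look safest. The direction depends on which cohorts are flagged and can reverse (step 6). The documents also do not treat the overview as the main DLT result, and they base RP2D selection on the totality of the data.
- A reader might take 2/6 = 33% against 2/12 = 17% as a crossing of the 25% escalation boundary. Two DLTs in 6 is a stay decision, which protocol Appendix 16.1 sends to a third cohort, and the pharmacodynamic cohort opens only at levels that have completed safety evaluation. The boundary applies to evaluable subjects only, so an All Treated percentage has no meaning against it.

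**What to change.** In SAP 8.2 and the shell of Table 14.3.1.2, print the DLT row as n/N, with N the number of DLT Evaluable subjects in that schedule and dose column. Apply the same rule in the pooled and all-subjects columns. Add a footnote naming the population, and check that the row matches Table 14.3.1.12. Alternatively, remove the row and refer the reader to Table 14.3.1.12.

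In either case, state whether DLT-type events are flagged in pharmacodynamic and expansion subjects. If they are, give them a separate, labelled row or listing so that they are not lost. Record the choice in SAP Section 11.

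The cost is a sentence or two in the SAP and a small change to one table shell, plus a row or listing if events are flagged outside escalation. No other planned analysis changes.
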